15.1.2 Delayed Rituximab

Note that calendar resets for each course of delayed rituximab.

Time point	MRD ¹	w1	w2	w3	w4	w5 +/- 4 days	w6	w7	w8
Treatment									
Rituximab		X	X	X	X	X	X	X	X
Procedures									
Bone Marrow Biopsy ²	X	X							
HCL Imaging ³	X								
EKG	X								
History & Physical	X					X			
Laboratory Evaluations									
Amylase, lipase, GGT, lipid panel, TSH, free T3, free T4, ferritin, PCR, IgG, IgA, IgM, haptoglobin, CRP, chemistries ¹²	X	X							
FACS ⁵	X					X			
Urinalysis	X	X							
CBC, Diff	X	X	X	X	X	X	X	X	X
Research Evaluations⁷									
PaxGene ⁵	X					X			
Tumor markers	X	X ⁶	X ⁶	X ⁶	X ⁶	X	X ⁶	X ⁶	X ⁶
TBNK	X ⁶	X ⁶	X ⁶	X ⁶	X ⁶	X	X ⁶	X ⁶	X ⁶

¹ MDR+ is the time point that MRD is detected after cladribine.² New bone marrow biopsy is needed before delayed rituximab if none for >6 months³ CT neck-pelvis or abdominal MRI needed only before cladribine. If no nodes, all subsequent imaging may be done with spleen U/S (or abdominal U/S if no spleen), including baseline for delayed rituximab⁴ Chemistries=albumin, alkaline phosphatase, ALT, AST, bilirubin, BUN, calcium, CK, chloride, CO2, creatinine, direct bilirubin, glucose, potassium, LDH, magnesium, sodium, phosphorus, total protein, uric acid⁵ Needed if >28 days from last FACS and PaxGene⁶ When patients are at NIH

⁷ Samples collected during the course of this study will be stored, tracked, and disposed of as specified in investigator's companion protocol, 10-C-0066, on which all subjects will be co-enrolled

15.1.3 Follow up (Post-Treatment) - After Cladribine or Delayed Rituximab

Time point	w9 +/- 7 days	3m +/- 2 wks	6m ¹⁰ +/- 1m	9m +/- 1m	1y +/- 1m	15m +/- 1m	1.5y +/- 1m	21m +/- 2m	2y +/- 2m	27m +/- 2m	2.5y +/- 2m	>2.5 y
Procedures												
Bone Marrow Biopsy ¹			X				X				X	X ⁵
MRI ²			X				X				X	X ⁵
HCL Imaging ³			X				X				X	X ⁵
EKG			X				X				X	X ⁵
History & Physical			X				X				X	X ⁵
Laboratory Evaluations												
GGT, amylase, lipase, lipid panel, TSH, free T3, free T4, TSH, ferritin, PCR consensus, IgG, IgA, IgM, D-Dimer, haptoglobin, CRP, fibrinogen, chemistries ⁴			X				X				X	X ⁵
Urinalysis			X				X				X	X ⁵
CBC, Diff	X	X	X	X	X	X	X	X	X	X	X	X ⁶
FACS, TBNK ⁸		X	X	X	X		X		X		X	X ⁷
Research Evaluations⁹												
PaxGene, Tumor markers		X	X	X	X		X		X	X	X	X ⁷

¹ At NIH, aspirate for FACS, PCR-molecular diagnostics, and cloning/sequencing IgH rearrangements

² MRI of C- and T-Spine (only at NIH) may be cancelled at discretion of PI. MRI may be performed on all randomized and HCLv patients. Non randomized HCL classic patients will not have research MRIs performed

³ CT neck-pelvis or abdominal MRI needed only before cladribine. If no nodes, all subsequent imaging may be done with spleen U/S (or abdominal U/S if no spleen), including baseline for delayed rituximab

⁴ Chemistries=albumin, alkaline phosphatase, ALT, AST, bilirubin, BUN, calcium, CK, chloride, CO2, creatinine, direct bilirubin, glucose, potassium, LDH, magnesium, sodium, phosphorus, total protein, uric acid

⁵ Continue on an every 2 year schedule. Bone marrow biopsy may be skipped for patients no longer in CR.

Abbreviated title: CdA plus/minus Rituxan for HCL

Version date: 09/21/2022

⁶ Continue on an every 6 month schedule while in CR, otherwise every 3 months.

⁷ Continue on an annual schedule

⁸ Only do TBNK while if patient is at NIH

⁹ Samples collected during the course of this study will be stored, tracked, and disposed of as specified in investigator's companion protocol, 10-C-0066, on which all subjects will be co-enrolled

¹⁰ At NIH, unless allowed at another site at the discretion of the PI

15.2 APPENDIX B: EXAMPLES OF DETERMINATION OF REMISSION DURATIONS
 (MRD-free survival durations are presented in **Bold**).

A. Randomized to CdA + Rituximab, MRD negative after 2 months, no recurrence. Blood MRD-free survival: **> 23 months**.

↓ (Cladribine)

↓↓↓↓↓↓↓ (Rituximab qWk x8, begin C1D1)

(months from C1D1)

1	2	3			6			9			12			15			18			21			24	
+	-	-			-			-			-			-			-			-			-	

(MRD Status)

B. Randomized to CdA + Rituximab, MRD negative after 6 months, recurrence of MRD at 15 months, delayed rituximab at 16 months, MRD negative at 17 months, no recurrence.

Blood MRD-free survival: **>24 months**.

↓ (Cladribine)

↓↓↓↓↓↓↓ (Rituximab)

↓↓↓↓↓↓↓ (Rituximab)

1	2	3			6			9			12			15			18			21			24	
+	+	+			-			-			-			+	+	-	-	-		-			-	

C. Randomized to CdA + Rituximab, MRD negative after 1 month, recurrence of MRD after 2 months, delayed rituximab at 6 months, MRD negative at 12 months, recurrence of MRD at 24 months.

Blood MRD-free survival: **24 months**.

↓ (Cladribine)

↓↓↓↓↓↓↓

↓↓↓↓↓↓↓ (Rituximab)

1	2	3			6			9			12			15			18			21			24	
-	+	+			+	+	+	+			-			-			-			-			+	

D. Randomized to CdA alone, MRD positive at 3 and 6 months, rituximab given at 6 months, no recurrent MRD

Blood MRD-free survival: **>24 months.**

↓ (Cladribine)

↓↓↓↓↓↓↓ (Rituximab)

1	2	3			6			9			12			15			18			21			24	
+	+	+			+	+	+	-			-			-			-			-			-	

E. Randomized to CdA alone, MRD cleared by 6 months, recurred at 12 months, began rituximab at 12 months, no recurrent MRD.

Blood MRD-free survival: **>24 months.**

↓ (Cladribine)

↓↓↓↓↓↓↓ (Rituximab)

1	2	3			6			9			12			15			18			21			24	
+	+	+			-			-			+	+	+	-			-			-			-	

F. Randomized to CdA alone, MRD cleared by 1 month, recurred at 9 months, began rituximab at 10 months, still MRD+ by 16 months, began 2nd course of delayed rituximab at 17 months, and still MRD- at 24 months.

Blood MRD-free survival: **>24 months.**

↓ (Cladribine)

↓↓↓↓↓↓↓ (Rituximab)

↓↓↓↓↓↓↓ (Rituximab)

1	2	3			6			9			12			15			18			21			24	
-	-	-			-			+		+	+	+		+		+	-		-			-		

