1.1.2 Secondary Objectives

- To compare cladribine + rituximab vs. cladribine alone in terms of 1) initial MRD-free survival and disease-free survival, 2) response to delayed rituximab for relapse, to determine if early rituximab compromises later response, and 3) feasibility of administration as an outpatient by simultaneous rituximab beginning before the cladribine in nonrandomized HCL patients.
- To determine if MRD levels and tumor markers (soluble CD25 and CD22) after cladribine and/or rituximab correlate with response and clinical endpoints.
- To compare blood MRD-free survival in patients who receive cladribine and up to 2 courses of rituximab, with respect to whether the 1st course of rituximab was used simultaneous with cladribine.
- To determine, using MRD and tumor marker data, when bone marrow biopsy (BMBx) can be avoided in managing HCL.
- To compare response and MRD after the 1st and 2nd courses of cladribine.
- To evaluate the effects of cladribine and rituximab on normal T- and B-cells.
- To enhance the study of HCL biology by cloning, sequencing and characterizing monoclonal immunoglobulin rearrangements.

- To determine overall survival, particularly in patients with poor-prognosis HCL like HCLv.
- To correlate bone marrow MRI signal with bone marrow biopsy

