1.3.2 Endpoints to test simultaneous vs. delayed rituximab

The primary endpoint is whether simultaneous cladribine and rituximab cause a lower rate of MRD at 6 months than cladribine alone. Based on studies of rituximab for MRD after CdA [41, 47], CR

without MRD should be achieved in > 90% at 6 months after cladribine + rituximab. CR without MRD should be about 40-60% after cladribine alone, depending on whether or not patients had prior cladribine [11, 39, 40, 42-46]. However, a significant difference at 6 months would not indicate superiority in the clinical outcome of simultaneous cladribine + rituximab over cladribine alone, since delayed rituximab after 6 months might work better if it had not been used previously. Therefore, the major secondary endpoint will be to assess blood MRD-free survival not only after cladribine, but also after up to 2 rituximab courses given if needed for MRD in blood. BMBx IHC, blood and bone marrow aspirate FACS will be used for detecting MRD for the primary endpoint. However, since non-compliance with BMBx is expected to increase with longer follow-up, MRD-relapse for the secondary endpoints for need for delayed rituximab will need to be determined by blood tests, either blood FACS positivity or presence of cytopenias (ANC < 1500/ul, Plt < 100,000/ul, or Hgb < 11 g/dl). Patients FACS-negative in both blood and bone marrow aspirate are considered in MRD-negative CR regardless of blood counts. FACS, consensus PCR and IHC are all CLIA certified tests. Patients with 'dry' bone marrow or bone marrow unable to be aspirated will be considered MRD+, since in MRD-free CR, the bone marrow aspirate should be liquid and able to be aspirated. RQ-PCR, which is the most sensitive test, will also be observed, but will not be used for clinical decisions or statistics because it is early in its development, particularly in following HCL after chemotherapy. If patients achieve significantly longer time MRD-free survival after cladribine + rituximab than after cladribine alone, but shorter MRD-free survival after delayed rituximab if rituximab was used previously with cladribine, this will argue against changing the standard treatment for HCL from cladribine alone. The delayed rituximab in the trial design also permits several secondary scientific objectives (see Section 1.1.2) to be investigated for rituximab alone, including 1) determining if MRD levels and tumor markers (soluble CD25 and CD22) after rituximab correlate with response and tumor burden, 2) determining if BMBx can be avoided for judging response in HCL after rituximab, and 3) determining the effect of rituximab on normal B-cells without interference from simultaneous or recent cladribine.

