6.2 SECONDARY ENDPOINTS

In addition to the primary goal of determining differences in the MRD level according to rituximab administration, the following goals will also be explored in patients on this study.

The most important secondary endpoints are MRD-free survival after cladribine, and MRD-free survival after up to 2 courses of rituximab. For the secondary endpoints of this protocol, and for triggering delayed rituximab, patients with or without CR are considered MRD+ if the blood FACS is positive or if low blood counts become inconsistent with CR (ANC < 1500/ μ l, Plt < 100,000/ μ l, or Hgb < 11). Patients FACS-negative in both blood and bone marrow aspirate are considered MRD-negative regardless of blood counts. Failure of cladribine and/or rituximab to clear MRD by blood FACS requires that this test be positive at 6 months since MRD at 1-3 months may clear by 6 months. However, MRD relapse will be considered when first detected, even if before 6 months, if cladribine and/or rituximab fail to clear MRD at 6 months. If simultaneous cladribine and rituximab is superior to cladribine and delayed rituximab, MRD-free survival after cladribine and after delayed rituximab should together be longer if cladribine was combined with rituximab than if used alone. In order to compare the probability of development of MRD as a function of time according to whether rituximab is used immediately or not, Kaplan-Meier curves for this endpoint will be created, beginning at the date of randomization, and compared using a two-tailed log-rank test. Patients who develop MRD will be considered to have had an event for the actuarial curve, while those without MRD found in this manner will be considered censored and will remain in follow-up for this endpoint. With each stratum considered separately, or if both strata are combined, the power for this comparison will potentially be low, but the results may demonstrate a trend if one is present. Measurement of best response to cladribine vs. cladribine + rituximab will also be done at 1 and 6 months after cladribine. The CR and PR rates will be reported, as well as appropriate 95% exact confidence intervals.

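### Section 6.2 names two MRD-free survival endpoints but writes one event rule, which fits only the first; the rule Appendix B follows for the second is stated nowhere

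*Combined protocol and SAP*

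**What the plan says.** Section 6.2 states: "The most important secondary endpoints are MRD-free survival after cladribine, and MRD-free survival after up to 2 courses of rituximab". Section 1.1.2 lists the cumulative comparison as its own objective ("To compare blood MRD-free survival in patients who receive cladribine and up to 2 courses of rituximab"). Section 1.3.2 explains its rank: a 6-month difference alone would not establish a better clinical outcome, so "the major secondary endpoint will be to assess blood MRD-free survival not only after cladribine, but also after up to 2 rituximab courses".

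The analysis text in 6.2 then speaks of a single endpoint: "Kaplan-Meier curves for this endpoint will be created, beginning at the date of randomization, and compared using a two-tailed log-rank test". The event is "Patients who develop MRD will be considered to have had an event for the actuarial curve", and patients without MRD are censored. Two sentences deal with early positives: "Failure of cladribine and/or rituximab to clear MRD by blood FACS requires that this test be positive at 6 months", and "MRD relapse will be considered when first detected, even if before 6 months, if cladribine and/or rituximab fail to clear MRD at 6 months". Nothing says that MRD stops counting as an event when a further rituximab course is available.

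Appendix B prints one blood MRD-free survival time for each of six examples. It counts months from the first day of cladribine, states no rule, and does not say which endpoint it illustrates. Example F, "recurred at 9 months, began rituximab at 10 months, still MRD+ by 16 months, began 2nd course of delayed rituximab at 17 months", is printed as longer than 24 months.

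**The concern.** An endpoint that runs through up to two rituximab courses needs its own event: MRD after the last course the patient may receive. The only written event is first MRD. An analyst who follows 6.2 and one who follows Appendix B would score the same patient differently.

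The stake is the purpose given in Section 1.3.2. Under 6.2's rule, a patient still blood-MRD-positive at 6 months is already an event before any delayed rituximab. Used for the second endpoint, the rule reproduces the first curve and carries in the 6-month difference that this endpoint was meant to look beyond.

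Two smaller points bear on the same analysis. The FACS schedule in 6.1 differs from the calendar, which affects event dates. The log-rank test is not said to be stratified when the strata are combined.

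**Working it through.** **1. Appendix B's figures.** As printed: A >23, B >24, C 24, D >24, E >24, F >24 months. That is one event (C) and five censored.

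**2. Section 6.2's rule on the same histories.** If MRD is present at 6 months, the event is at the first positive test. Otherwise early positives are ignored and the event is the first positive after 6 months.

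| Example | MRD history | 6.2 rule (months) | Appendix B (months) |
|---|---|---|---|
| A | positive at 1, negative from 2 | no event | >23 |
| B | cleared by 6, recurs at 15 | 15 | >24 |
| C | positive at 2, 3 and 6; negative at 12; positive at 24 | 2 | 24 |
| D | positive at 1 to 3 and at 6, then clears | 1 | >24 |
| E | cleared by 6, recurs at 12 | 12 | >24 |
| F | negative to 6, recurs at 9 | 9 | >24 |

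The 6.2 rule gives five events against one and matches none of the six printed durations. Dating the 6-month failures at month 6 moves C and D to 6 months and still gives five events. For F only the dates in its sentence are used, because its status row cannot be aligned reliably in the text available.

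**3. The rule Appendix B appears to follow.** Take time from the first day of cladribine to MRD that persists at 6 months after the last permitted rituximab course began, or recurs after that. B and F have had two courses and are negative afterwards: >24. D and E have had one course and are negative afterwards: >24. C has had two courses, clears by month 12 and is positive at 24: event at 24. This matches event status in all six and duration in B to F. A should then be >24, but >23 is printed. Counting from the first negative test does not help: it gives A >22 and B >18.

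**4. Patients the implied rule does not score.** Section 3.3.1 bars retreatment after dose-limiting toxicity or excessive delay. Section 3.8.1 removes patients whose progression is judged too rapid for rituximab alone. Either may be MRD-positive with a course unused, and no example covers this.

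**5. Test schedule.** Section 6.1 plans MRD evaluations monthly for 3 months, 3-monthly for 2 years, then 6-monthly. The calendar (15.1.1 and 15.1.3) has FACS at week 5, at 3, 6, 9, 12, 18, 24 and 30 months, then annually. FACS is therefore absent at week 9, 15 months and 21 months. Blood counts, which also contribute to blood MRD, are scheduled at those three visits. On FACS alone, C's first MRD would be seen at 3 months instead of 2, and B's recurrence at 18 instead of 15.

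**6. Stratified log-rank.** The inputs are 34 + 34 and 31 + 31 patients, with assumed exponential times, hazard ratio 0.7, 120 months of follow-up and two-sided 5%, over 10,000 simulated trials. All stratum medians are assumptions.

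| Medians, 0 / 1 prior course (months) | Unstratified | Stratified | Gain (points) |
|---|---|---|---|
| 53 / 23 | 37.8% | 45.5% | 7.7 |
| 53 / 40 | 42.2% | 42.6% | 0.4 |
| 36 / 12 | 34.9% | 48.6% | 13.7 |

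The 53 and 23 months appear in 6.1 as remission and response durations, not blood-MRD times.

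**The case against.** The best defence is that Appendix B and 6.2's rule concern different endpoints. Sections 1.1.2 and 1.3.2 use the blood MRD-free survival label for the cumulative endpoint, and B to F match it. Section 6.2 also remarks that the periods after cladribine and after delayed rituximab should together be longer if the combination is superior, which hints at a cumulative measure. The single endpoint in its Kaplan-Meier sentence may well be the first one. All this stands, and it means five against one is mostly endpoint one against endpoint two. It does not supply the missing rule: none of these places gives the second endpoint an event, origin or censoring rule.

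A reader might go further in three ways that the documents do not support:

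- **That Appendix B hides events or favours an arm.** The six patients are constructed and both arms are scored the same way, so neither inference follows. Totals of MRD-positive months in these examples would likewise estimate nothing about the trial.
- **That the month-6 carry-over can be sized from 6.1.** The planning rates give 0.25 × 34 + 0.35 × 31 = 19.35 events against 0.05 × 34 + 0.10 × 31 = 4.8. Those rates cover any of three tests, two of them on marrow, while this endpoint uses blood.
- **That follow-up misses blood MRD at the visits without FACS.** Low counts also qualify and blood counts are taken, so only FACS frequency is in conflict.

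It is also fair that A's discrepancy is one month and does not change its event status.

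**Conclusion.** The second of the two main secondary endpoints has no written event rule. The one rule in 6.2 fits the first endpoint. Read onto the second, it would duplicate the first and contradict the worked examples: five events against one in the six cases. That contrast shows that the rules measure different quantities, and nothing more. The reading of Appendix B as the second endpoint is an inference from its label and from B to F.

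The weight is minor to moderate. Section 6.2 itself says that power may be low, the secondary analyses are exploratory and unadjusted, and the 6-month primary endpoint is unaffected. The FACS schedule conflict is real but partly covered by blood counts. Stratifying is a small improvement, worth from about nothing to 14 points of power under the assumed inputs.

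**What to change.** 1. In 6.2, keep the present rule for MRD-free survival after cladribine and define the second endpoint separately: time from randomization to MRD after the last permitted rituximab course. State how to score an MRD-positive patient who does not receive the next permitted course (for example, as an event at that MRD date) and how to treat death without MRD. Label Appendix B as illustrating this endpoint, use the same origin there, and correct or explain A.
2. Reconcile the MRD test schedule in 6.1 with the FACS visits in the calendar.
3. When strata are combined, stratify the log-rank test by prior purine analog, the randomization stratum in 2.3.2.

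Optionally, report the proportion blood-MRD-negative at fixed times from randomization. This needs a stated window, because FACS is annual after 2.5 years and the calendar resets with each delayed course.

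The cost of items 1 to 3 is wording. No endpoint is removed and stratifying needs no new data. The wording should be settled before blood-MRD times are examined by arm.

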15.3 APPENDIX C: PERFORMANCE STATUS CRITERIA

ECOG Performance Status Scale		Karnofsky Performance Scale	
Grade	Descriptions	Percent	Descriptions
0	Normal activity. Fully active, able to carry on all pre-disease performance without restriction.	100	Normal, no complaints, no evidence of disease.
		90	Able to carry on normal activity; minor signs or symptoms of disease.
1	Symptoms, but ambulatory. Restricted in physically strenuous activity, but ambulatory and able to carry out work of a light or sedentary nature (e.g., light housework, office work).	80	Normal activity with effort; some signs or symptoms of disease.
		70	Cares for self, unable to carry on normal activity or to do active work.
2	In bed <50% of the time. Ambulatory and capable of all self-care, but unable to carry out any work activities. Up and about more than 50% of waking hours.	60	Requires occasional assistance, but is able to care for most of his/her needs.
		50	Requires considerable assistance and frequent medical care.
3	In bed >50% of the time. Capable of only limited self-care, confined to bed or chair more than 50% of waking hours.	40	Disabled, requires special care and assistance.
		30	Severely disabled, hospitalization indicated. Death not imminent.
4	100% bedridden. Completely disabled. Cannot carry on any self-care. Totally confined to bed or chair.	20	Very sick, hospitalization indicated. Death not imminent.
		10	Moribund, fatal processes progressing rapidly.
5	Dead.	0	Dead.

15.4 APPENDIX D: NEW YORK HEART ASSOCIATION CLASSIFICATION

Class	Patient Symptoms
Class I (Mild)	No limitation of physical activity. Ordinary physical activity does not cause undue fatigue, palpitation, or dyspnea (shortness of breath).
Class II (Mild)	Slight limitation of physical activity. Comfortable at rest, but ordinary physical activity results in fatigue, palpitation, or dyspnea.
Class III (Moderate)	Marked limitation of physical activity. Comfortable at rest, but less than ordinary activity causes fatigue, palpitation, or dyspnea.
Class IV (Severe)	Unable to carry out any physical activity without discomfort. Symptoms of cardiac insufficiency at rest. If any physical activity is undertaken, discomfort is increased.

15.5 APPENDIX E: GUIDELINES FOR RITUXIMAB PREPARATION AND ADMINISTRATION

15.5.1 How Supplied

Rituximab will be supplied in 50-mL vials containing 500 mg of antibody (50 mL of solution) at a concentration of 10 mg/mL and 10-mL vials containing 100 mg of antibody (10 mL of solution) at a concentration of 10mg/ML. Rituximab vials are sterile, preservative-free, and intended for single use only.

15.5.2 Stability and Storage

Rituximab is biologically and chemically stable at 2°C to 8°C (36°F to 46°F) and has a proposed shelf-life stability of 30 months. Once reconstituted into IV bags, rituximab is chemically stable for up to 24 hours at 2°C to 8°C (36°F to 46°F), followed by up to 24 hours at room temperature (23°C). However, since rituximab solutions do not contain preservative, diluted solutions should be stored refrigerated (2°C to 8°C). No incompatibilities between rituximab and polyvinylchloride or polyethylene bags have been observed. Rituximab vials should be protected from direct sunlight. Rituximab vials are intended for single use only. Do not use beyond the expiration date stamped on the carton.

